Specific Aim 2: To investigate the correlation between myocardial perfusion measured using CT-MPI and PET-CT MPI, and coronary flow measured using CT-FFR.

Specific Aim 3: To compare the accuracy of PET-CT MPI and combined CT-MPI / CT-FFR approach in the detection of myocardial perfusion abnormalities and coronary stenosis.

B. BACKGROUND AND SIGNIFICANCE

Myocardial perfusion imaging (MPI) is a well-researched technique to evaluate myocardial ischemia. Originally started as a technique limited to nuclear imaging techniques such as Single Photon Emission Computerized Tomography (SPECT) and Positron Emission Tomography (PET), MPI has become available for Computed Tomography (CT) as a result of technological developments. PET-MPI and CT-MPI are the only two techniques that allow for the absolute quantification of myocardial blood flow, directly calculated from the myocardium. Absolute quantification of myocardial perfusion is not only able to quantify lesion specific ischemia but also able to identify global ischemia and microvascular abnormalities, this in contrast to MPI using other modalities (1,2). Some research even implies that subclinical changes, caused for example by diabetes and hypertension, can be detected (2).

The main reason that PET and CT are able to quantify myocardial perfusion is the linear relationship between myocardial blood flow and myocardial tracer/contrast uptake. In figure 3, the relationship between PET and SPECT tracers is shown, where the PET tracers clearly show an superior relationship compared to the SPECT tracers (3). Although both iodine and gadolinium are considered extracellular contrast agents, the advantage of iodine is that the relationship between contrast agent concentration and the change in signal intensity is linear over a wide range and contrast agents concentrations are thus strictly proportional to the signal enhancement, see figure 4 (4). For SPECT tracers as well as gadolinium, used for MRI MPI, the relationship becomes non-linear at higher myocardial blood flows (3,5,6) making absolute quantification impossible.

[figure not shown]

Figure 3. Kinetics of MPI perfusion tracers. Graphical presentation of the relationship between absolute Myocardial Blood Flow (MBF) of the several PET radiotracer and actual tracer uptake.

[figure not shown]

Figure 4. Attenuation density versus iodine concentration. Note the linear relationship even at higher concentrations of iodine (HU: Hounsfield units).

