CT is the latest modality that's being able to perform MPI. Traditionally, this technique was limited by the low temporal resolution and high radiation dose of CT systems, however, on current high-end

systems CT MPI is now possible at equal or even lower radiation doses than the nuclear equivalent. One of the issues with CT MPI is the wide variety of protocols, systems and models used resulting in a wide variety of absolute myocardial blood flow (MBF) values with corresponding ranges of threshold values (7–9). Another issues encountered when comparing CT-MPI to perfusion imaging with other modalities are the significantly lower MBF values measured with CT-MPI (10). Currently, the mathematical models used to calculate MBF, are directly extracted from MRI perfusion studies and an optimal model for CT-MPI has not been determined. Comparing CT-MPI to PET-MPI would help gain insight in the ability of CT to quantify myocardial blood, what the optimal imaging protocol and tracer kinetic model is and is needed to give CT-MPI the last push into clinical implementation on a wide scale.

Another option to evaluate the functional significance of coronary artery disease is measuring the fractional flow reserve (FFR). Fractional flow reserve has been used to measure the functional consequences of specific lesions by measuring a pressure gradient over this lesion, assuming that a drop in pressure will result in an corresponding drop in coronary blood flow and thereby impairing the blood flow to the myocardium (10). This technique has been hampered by the high cost and invasiveness of the procedure. More recently a new approach to calculate FFR has been developed, CT derived FFR (CT-FFR). With the use of computational fluid dynamic and optionally the use of artificial intelligence, it is now possible to calculate FFR from regular CCTA images and anatomically and functionally evaluate the significance of a lesion (11). Several studies have proved the excellent diagnostic accuracy of CT derived CT-FFR with the use of AI, either compared to invasive FFR or in comparison with computation fluid dynamics derived CT-FFR (12–16).

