Quantitative analysis of the PET-MPI and CT-MPI acquisition will be performed on per segment (AHA 17 segment model), per territory, per slice and per patient basis. Not only area specific MBF will be calculated but also global perfusion parameters will be taken into account. For the CT-MPI images, MBF will be calculated with different tracer kinetic models and using different temporal sampling rates in order to find the optimal protocol resulting in the highest diagnostic accuracy and lowest radiation dose possible. CT-FFR analysis as well as anatomical evaluation will be performed on all CCTA acquisitions, on per vessel as well as per patient level. Clinical data of the patients will be recorded, such as clinical risk factors, medication use etc. If the patients receive invasive coronary angiography (with or without invasive FFR measurements) or receive treatment after both PET-MPI and CT-MPI were performed, either medicational or interventional, this will be recorded. Readers will be blinded to the results of examinations.

D.2 Statistical Methods / Sample Size Justification

Statistical analysis and graphs will be performed with Sigma Stat 3.5, SigmaPlot 8.0, and Sample Power 2.0 (SPSS, Chicago, IL.). Disease information and demographic variables, such as age and sex, will be summarized by means of descriptive statistics. Data will be reported as means \pm SD or rates with 95 percent confidence intervals. A difference with P value of 0.05 or less will be considered significant. Sensitivity, specificity, accuracy, negative predictive value and positive predictive value will be estimated by using generalized estimating equations, assuming that all measurements in each individual vessel and for each person will be correlated interchangeably. Accuracy of CT-MPI compared with PET-MPI for

detection and grading (in percent of the myocardial slice or myocardial infarct) of perfusion deficit and reduction in myocardial function will be compared. P values for comparisons of reader specific values will be calculated by means of the McNemar test. Kappa analysis will be used to determine agreement for the detection and grading of myocardial ischemic insult and/or infarction during adenosine-stress. This is a preliminary and pilot study, with a convenience sample of 30 patients, that we deem adequate to demonstrate our hypothesis. The analysis includes patient-based analysis and coronary artery-based analysis.

E. PROTECTION OF HUMAN SUBJECTS

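### The CT-MPI kinetic model and sampling rate are chosen partly for highest accuracy in the same 30 patients used to estimate accuracy, with no correction, so accuracy quoted for the chosen combination is biased upward

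*Combined protocol and SAP*

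**What the plan says.** Image Analysis in section D.1 states that "MBF will be calculated with different tracer kinetic models and using different temporal sampling rates", and gives the purpose: "in order to find the optimal protocol resulting in the highest diagnostic accuracy and lowest radiation dose possible". Accuracy, jointly with radiation dose, is therefore the criterion for choosing among the combinations. The weight given to each is not stated.

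Section D.2 says "Sensitivity, specificity, accuracy, negative predictive value and positive predictive value will be estimated by using generalized estimating equations", and describes the sample: "This is a preliminary and pilot study, with a convenience sample of 30 patients". Section D.1 sets a target of 15 patients with significant CAD among the 30. There is no second cohort.

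The Background (section B) says that "an optimal model for CT-MPI has not been determined" and that earlier work produced "a wide variety of absolute myocardial blood flow (MBF) values with corresponding ranges of threshold values". Neither the model nor the cut-off can therefore be taken as settled from outside. The documents name no primary model or rate, list no candidates, give no MBF cut-off, and mention no hold-out set, cross-validation, bootstrap or multiplicity rule.

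**The concern.** Each candidate's observed accuracy is its true accuracy plus sampling error. Choosing the candidate that looks best favours those whose error happened to be positive, so the winner's observed accuracy exceeds its true accuracy on average. GEE allows for correlation among vessels and segments within a patient. It does nothing about selection.

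Accuracy is something this study sets out to deliver. Aim 3 is "To compare the accuracy of PET-CT MPI and combined CT-MPI / CT-FFR approach" in detecting perfusion abnormalities and stenosis, and section E.4 offers diagnostic accuracy as the knowledge to be gained. The Background describes the comparison with PET as "needed to give CT-MPI the last push into clinical implementation on a wide scale". An inflated figure from this study could become the planning value for the next one. If the MBF cut-off is also derived from these data, a second source of optimism is added.

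**Working it through.** **The plan's own figure.** The sample of 30 is a convenience number with no inputs, so there is nothing to reproduce. Its precision can be stated: for an observed accuracy of 0.80, the Wilson 95% interval is 0.63-0.90 with n = 30.

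**Inputs.** From the documents: 30 patients, selection on accuracy and dose, and no correction. Assumed: 15 PET-positive and 15 PET-negative (borrowed from the CAD target, since PET-positive numbers are not given), PET as the reference for selection, AUC 0.80-0.90, correlation between candidates' MBF values 0.8-0.95, and 2, 4 or 12 candidates.

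**One candidate.** In a binormal model with AUC 0.85, the separation is d = √2 × Φ⁻¹(0.85) = 1.466. With the cut-off fixed at the true midpoint, accuracy is Φ(d/2) = Φ(0.733) = 0.768. Its standard error is √(0.768 × 0.232 / 30) = 0.077, or 7.7 points.

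**Best of K equal candidates.** Approximately, bias = SE × √(1 − r) × c_K. Here r is the correlation between two candidates' correct/incorrect calls, and c_K is the expected maximum of K independent standard normals (0.564, 1.03 and 1.63 for K = 2, 4 and 12). With MBF correlation 0.8, the chance that both candidates are correct is about 0.691, so r = (0.691 − 0.768²)/(0.768 × 0.232) ≈ 0.57. Then:

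- K = 2: 7.7 × 0.656 × 0.564 ≈ 2.8 points
- K = 4: 7.7 × 0.656 × 1.03 ≈ 5.2 points
- K = 12: 7.7 × 0.656 × 1.63 ≈ 8.2 points

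Simulation, which respects the discreteness of 30 patients, gives 2.9, 5.0 and 7.8-7.9. For K = 12 the winner appears to have accuracy 84.7% against a true 76.8%.

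**Simulated bias in points, cut-off fixed in advance:**

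| Setting | 2 candidates | 4 | 12 |
|---|---|---|---|
| Equal candidates, AUC 0.80-0.90 | 1.7-3.0 | 3.3-5.4 | 4.9-8.4 |
| Unequal candidates, AUC 0.75-0.90 | 0.2-0.4 | 1.7-3.0 | 3.6-6.0 |

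Variations:

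- Lowest-dose candidate within one or two patients (3.3 or 6.7 points) of the best, 4-12 candidates: 2.2-7.8.
- Territory level, 3 × 30 = 90 territories: 1.2-5.6.
- 8, 10 or 20 of the 30 PET-positive: 1.9-9.2.

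**A different model.** Drawing correct/incorrect calls from a latent Gaussian with true accuracy 0.80 and 6 candidates gave a bias of 7.4 to 4.9 points for correlation 0.5 to 0.9. With true accuracies spread over 0.72-0.82, the truly best of 6 was picked only 30-37% of the time.

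**Cut-off tuned on the same data.** Total bias is 6.5-13.6 points. Of this, 6.4-7.8 arises from the cut-off with no model selection at all, so it is a separate contribution and is not counted in the figures above.

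**Does the remedy work?** With AUC 0.85 and 4 or 12 candidates, nested 5-fold cross-validation stratified by PET result came within 0.7 points of the true value in all 8 settings. Leave-one-patient-out came within 0.4 with a fixed cut-off, but was 1.5-2.4 too high with a tuned one. A simple bootstrap optimism correction left 1.7-3.2 points (fixed) or 4.0-5.9 (tuned). These checks used 250-500 trials. With a per-trial SD near 8 points, the simulation error is 8/√500 to 8/√250, about 0.36-0.51, so residuals of this size are close to noise.

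**The case against.** - **The plan never says that the winner's accuracy will be the reported result.** This is true, and some D.2 analyses (McNemar, kappa) are reader-based. The point is therefore limited to accuracy quoted for the chosen combination. Section D.2 does not exclude that or label it exploratory.
- **The size rests on assumptions and can be small.** This stands. If sampling rates are produced by thinning one acquisition, which is not stated, candidates could correlate at 0.99. The bias for equal candidates then falls to about 1, 2 and 3-3.5 points for 2, 4 and 12 candidates. With one clearly better candidate at that correlation it is 0.1-0.3. The direction does not change.
- **Aim 3 cannot use PET as its sole reference, because PET is one of the tests compared.** This also stands, and it dilutes the effect. In a run with 7.8 points of bias against PET, 3.3-6.3 remained when the other reference agreed with PET in 70-90% of patients. The combined CT-MPI/CT-FFR reading was not simulated.
- **Sampling error in a pilot exceeds this bias.** Coverage of the unadjusted 95% interval does stay near 94-96% with 6 candidates, and drops to 85-92% only with 20. But sampling error is disclosed by the interval and has no direction, whereas this bias always points upward and is disclosed nowhere. A pilot label justifies exploring but corrects nothing.
- **Nested cross-validation estimates the performance of the selection procedure, not of one fixed combination.** This is correct, and the report should describe it in that way.

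**Conclusion.** The concern holds. If the plan is followed as written, accuracy quoted for the chosen model and sampling rate is too high on average, and its interval is centred too high. Any Aim 3 comparison that uses the chosen CT-MPI reading inherits some of this.

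The direction follows from selecting on accuracy in a single sample. The size cannot be derived from the documents, because the number of candidates, their correlation and their true accuracy are not given. Under the stated assumptions with a fixed cut-off and equal candidates, it runs from about 2 points with two candidates to about 8 with twelve. It is smaller for unequal or very highly correlated candidates, and larger only if the cut-off is tuned as well. The study remains sound as a pilot. This is a correction that should be made, not a fatal flaw.

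**What to change.** Before PET results are linked to the CT data, add to section D.2:

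1. One primary kinetic model and sampling rate, whose accuracy then needs no correction for selection.
2. A list of the other candidates, with an explicit rule for trading accuracy against radiation dose when choosing among them.
3. The source of the MBF cut-off.
4. Nested cross-validation for every choice left open (model, rate or cut-off), applying the written rule inside each fold and keeping all segments and vessels of a patient together. Leave-one-patient-out is adequate if the cut-off is fixed. If it is tuned, use repeated 5-fold stratified by PET result. A simple bootstrap correction is not enough at this sample size.
5. Reporting: show all candidates, give the cross-validated figure as the accuracy of the selection procedure, and label the best apparent accuracy exploratory.

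The simplest version is items 1 and 3 with a cut-off fixed in advance and everything else labelled exploratory. Item 4 is needed only if a selected combination's accuracy is to be quoted.

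The cost is SAP wording and some analysis code, with no new patients or scans. The reported accuracy will probably be lower.

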clinically established PET-CT and CT-MPI protocols with the administration of iodinated contrast media. The goal is to include 30 patients, of which 15 should have significant CAD.

PET-MPI Protocol

Patients with suspected CAD who are referred to a clinical PET-MPI will undergo the standard clinical protocol applied in the Emory Nuclear Medicine department. For technical details, please see the PET protocol form included as additional material in the section F.

CT-MPI and CT-FFR Protocol

Image Acquisition

The CT protocol will consist of a CT-MPI acquisition followed by a coronary CT angiography (CCTA) acquisition for the FFR assessment, and it will be performed on a 3rd generation dual-source scanner (Siemens Force) located in the Emory Tower. The CT-MPI acquisitions will be performed first to avoid interference of contrast agent contamination. Between the CT-MPI acquisition and the CCTA will be an adequate time interval to allow the outflow of contrast agent and for the patient to return to a full rest state. CT-MPI will be performed under stress, using the same stressor agent used in the PET-MPI examination to ensure optimal comparison conditions.

For the CT-MPI, dynamic volume CT myocardial perfusion applying the “dynamic shuttle” mode will be used to rapidly cover the entire cardiac anatomy during infusion of a contrast medium bolus for monitoring bolus passage through the left ventricular myocardium. The “dynamic shuttle” mode consists of an image acquisition during rapid, yet smooth back-and-forth movement of the CT scanner table, so that contrast media bolus passage can be evaluated within the entire left ventricle in a time-resolved fashion. This scan acquisition will be performed during pharmacologically induced stress and during rest conditions. CT-MPI studies will be contrast medium enhanced by 50-70 ml of iodinated contrast agent,

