Subjects will be monitored in clinic as per clinical standard practice for any possible side effects and treated as indicated.

E.3 POTENTIAL BENEFITS OF THE PROPOSED RESEARCH TO THE SUBJECTS AND OTHERS

Since the CT examinations in this study are performed for research purposes and are not used for diagnostic purposes, there are no direct benefits for study participants. However, the knowledge gained from this study may benefit future patients undergoing CT-MPI and CT-FFR.

Compensation to Participants

Participants will be compensated with a \$200.00 gift card to cover for parking, travel costs etc.

E.4 IMPORTANCE OF THE KNOWLEDGE TO BE GAINED

Knowledge gained during this study will enable an appreciation of the diagnostic accuracy of CT-MPI and CT-FFR in comparison to PET-MPI for diagnosis of coronary artery disease and give indications of potential impacts on clinical and diagnostic pathways. Furthermore, the diagnostic value of cardiac CT imaging in detection coronary stenosis may be improved.

E.5 SUBJECT SAFETY AND MINIMIZING RISKS (Data and Safety Monitoring Plan)

Eligibility in each case will be confirmed by a named investigator. The source data will be collected by an independent technician and/or study coordinator, maintained securely by the PI and checked by the named investigators. Clinical data will be recorded on a Case Report Form (CRF). However, formal monitoring of site records will not be completed as part of the general conduct of the study. Data collected will be authentic, accurate and complete and the study will be conducted in accordance with the currently approved protocol (and any future approved amendments), Good Clinical Practiced (GCP) and all applicable regulatory requirements.

Any event meeting the criteria of an unanticipated problem involving risks to subjects or others will be reported to the Emory IRB, as required by HRPP 4.7- Unanticipated Problems and Adverse Events Policy and Procedures. Clinical data will not be monitored by a 3rd party (i.e. Clinical Research Associate (CRA)) or sponsor but the results of the study will be written up as a paper and may be submitted as abstracts to various conferences. Every effort will be made to ensure patient safety and confidentiality.

F. ADDITIONAL MATERIAL

PET MPI Clinical Protocol

PROCEDURE TITLE: Rubidium PET Myocardial Perfusion Imaging

APPLICABLE FACILITIES: (Check all that apply)

EUH EUOSH EWWH EUHM EJCH ESJH TEC ESA ERH

EFFECTIVE DATE: 1/9/2019

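### D.2 measures diagnostic accuracy only at unstated cut-offs and plans no ROC analysis, although stress MBF and CT-FFR are continuous and the protocol says CT MBF thresholds vary widely

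*Combined protocol and SAP*

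**What the plan says.** Section D.2 gives the accuracy measures: "Sensitivity, specificity, accuracy, negative predictive value and positive predictive value will be estimated by using generalized estimating equations", with correlation within vessel and person allowed for. For readers it adds: "P values for comparisons of reader specific values will be calculated by means of the McNemar test". For agreement: "Kappa analysis will be used to determine agreement for the detection and grading of myocardial ischemic insult and/or infarction". It also mentions grading the deficit as a percentage, but names no estimator for it. No ROC curve or AUC appears, and no positivity cut-off is stated for CT-MPI, CT-FFR or PET.

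The measurements themselves are continuous. The Image Analysis part of D.1 has MBF quantified at several levels from segment to patient, and CT-FFR by vessel and by patient. It also has MBF computed under several kinetic models and sampling rates, to find the protocol with the best accuracy and lowest dose.

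Section B describes the variety of CT-MPI protocols, systems and models as "resulting in a wide variety of absolute myocardial blood flow (MBF) values with corresponding ranges of threshold values", and adds that CT reads lower than other modalities. Section E.4 says the study will inform on the "diagnostic accuracy of CT-MPI and CT-FFR in comparison to PET-MPI".

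On size, D.1 says: "The goal is to include 30 patients, of which 15 should have significant CAD". D.2 calls the study a pilot "with a convenience sample of 30 patients, that we deem adequate to demonstrate our hypothesis".

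**The concern.** A sensitivity or specificity exists only once someone has decided which MBF or CT-FFR value is abnormal. The plan does not say who decides, when, or from what data. For MBF, Section B itself weakens the case for borrowing a published threshold, so the natural course is to look for a good cut-off in the study's own patients. The search over kinetic models and sampling rates for the highest accuracy adds a second choice made on the same data, and no validation sample is planned.

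Two things are at stake. Accuracy reported at a cut-off tuned to 30 patients will be too high, and a pilot's estimates are likely to be carried into later studies. Reducing a continuous measurement to yes or no also discards information when CT-MPI, CT-FFR and their combination are compared. An AUC needs no index-test cut-off and uses data already collected.

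**Working it through.** The plan gives no power, effect size or expected accuracy, so there is no figure of its own to reproduce.

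**Inputs from the documents.** 30 patients, 15 with significant CAD as a goal (D.1); significance at P of 0.05 or less (D.2), taken as two-sided.

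**Assumptions.** 15 reference-positive and 15 reference-negative patients; normal scores with equal variance; correlation 0.5 between two index tests; AUC values as listed; 4,000 simulated studies per setting for the paired comparison and 2,000 for the cut-off search.

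**Step 1. From AUC to accuracy.** With separation d in SD units, AUC = Φ(d/√2). At the ideal midpoint cut-off, sensitivity = specificity = Φ(d/2).
- AUC 0.90: d = √2 × 1.282 = 1.81, accuracy Φ(0.906) = 0.82.
- AUC 0.75: d = √2 × 0.674 = 0.95, accuracy Φ(0.477) = 0.68.

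**Step 2. Optimism from a cut-off chosen in the data.** Taking the best-fitting cut-off in each simulated study gives mean apparent accuracy 0.87 against a true 0.82 (5 points), and 0.75 against 0.68 (7 points).

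The same was done for (sensitivity + specificity)/2 at the Youden cut-off, with one MBF method and with the best of 4 or 6 methods (assumed correlation 0.8 between methods):

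| d (AUC) | Best attainable | Apparent, 1 method | Apparent, best of 4 | Apparent, best of 6 |
|---|---|---|---|---|
| 0 (0.50) | 0.500 | 0.599 | 0.635 | 0.646 |
| 0.74 (0.70) | 0.644 | 0.716 | 0.756 | 0.765 |
| 1.06 (0.77) | 0.702 | 0.762 | 0.807 | 0.815 |
| 1.35 (0.83) | 0.750 | 0.806 | 0.844 | 0.852 |
| 1.68 (0.88) | 0.800 | 0.850 | 0.885 | 0.892 |

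Where there is real discrimination, the excess with one method runs from 0.850 − 0.800 = 5.0 points to 0.716 − 0.644 = 7.2 points. With the best of 4 to 6 methods it runs from 0.885 − 0.800 = 8.5 points to 0.765 − 0.644 = 12.1 points. The chosen cut-off also truly performs slightly below the best one: 0.683 against 0.702 at d = 1.06 with one method.

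**Step 3. Cost to a paired comparison of two index tests.** The continuous analysis is the DeLong test of the AUC difference. The binary analysis is McNemar on correct versus incorrect calls at the true best cut-off.

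| True AUCs | DeLong | McNemar, asymptotic | McNemar, exact |
|---|---|---|---|
| 0.90 vs 0.66 | 75% | 50% | 39% |
| 0.90 vs 0.75 | 42% | 28% | 18% |
| 0.90 vs 0.80 | 20% | 15% | 8% |
| 0.90 vs 0.85 | 6% | 7% | 3% |

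Share of power lost at 0.90 vs 0.75: 1 − 28/42 = 33% asymptotic, 1 − 18/42 = 57% exact. At 0.90 vs 0.66: 1 − 50/75 = 33% and 1 − 39/75 = 48%. At 0.90 vs 0.85 no analysis has useful power. With equal AUCs the DeLong test rejects 4.7% of the time at 0.75 and 2.5% at 0.90, so its advantage is not bought with false positives.

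**Step 4. Information lost when asking whether one test discriminates at all.** The asymptotic efficiency of the best cut-off is 2/π = 0.64, a loss of 36%. At 80% power and d = 1.0, 16 per group are needed for the continuous analysis and 26 for the binary one: 1 − 16/26 = 38%.

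**The case against.** The strongest reply is that the power loss concerns a test the plan does not contain. D.2 uses McNemar for readers, not for comparing CT-MPI with CT-FFR, and the study is a convenience-sample pilot with no stated power. The 15 patients with significant CAD are a recruitment goal; the term is undefined and is not equated with a positive PET. Vessel-level analysis has more, clustered, units. All of this stands, so Step 3 shows what the choice of measure can cost, not a shortfall in a powered comparison.

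Four stronger readings are tempting and are not supported:

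- A reader might infer that dichotomising wastes half the study's power or most of its information. Half appears only with the conservative exact test and clearly different AUCs; the asymptotic loss there is a third, and the single-test information loss in Step 4 is 36 to 38%.
- A reader might infer that D.2 is wholly binary. It also mentions percentage grading, kappa on grading, and means with SDs, though it names no continuous accuracy method.
- A reader might infer that no outside threshold can be used for either test, so both cut-offs must come from these patients. Section B speaks of MBF thresholds only; for CT-FFR the gap is simply that no cut-off is stated. Nor does the protocol say it will derive a cut-off from the data. It leaves the matter open.
- A reader might infer that the AUC removes all selection bias. It removes the cut-off part only. Picking the best of 4 to 6 methods still raises an apparent AUC from 0.70 to 0.75–0.76, and from 0.50 to 0.56–0.57. An AUC also needs a binary PET reference, and no PET rule is given.

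**Conclusion.** The point holds in a bounded form and should be acted on. All the named accuracy measures depend on cut-offs that the plan does not fix, and a cut-off-free measure is available from the same data.

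The firmer part is the optimism: about 5 to 7 points if the MBF cut-off is tuned in these patients, and about 9 to 12 points if the best of four to six methods is picked as well. This is conditional on the tuning taking place. It rests on 15/15, normality and equal variance, and the larger range also on the assumed number and correlation of methods.

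The efficiency part is softer: a third to about a half of the power of a paired comparison when AUCs differ as much as 0.90 against 0.75 or 0.66, and little in absolute terms when they are close. It rests on the same assumptions plus the assumed AUCs and correlation.

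**What to change.** In D.2:

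1. Add the AUC of continuous stress MBF and of CT-FFR as accuracy measures, against a PET positivity rule written down in advance. Compare index tests per patient with the paired DeLong test, and per territory or vessel with a bootstrap that resamples patients.
2. For the combined CT-MPI/CT-FFR score, use a combination fixed in advance, such as the mean of the standardised values, or a fitted model with bootstrap optimism correction. Avoid pooled leave-one-out scores: in simulation at 15/15 with two markers correlated 0.5, a true combined AUC of 0.78 appeared as 0.69, and 0.50 as 0.36. That would bias Aim 3 against the combination.
3. Name one primary kinetic model and sampling rate before CT results are linked to PET, or place that selection inside the bootstrap.
4. Keep sensitivity, specificity, PPV and NPV as secondary measures, at cut-offs fixed before linkage or reported as optimism-corrected.

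The cost is SAP wording and a little more analysis with standard code; no new data are needed. The AUC is less directly clinical than sensitivity and specificity, which are still reported. It is also imprecise at this size: the approximate 95% half-width at AUC 0.77 with 15/15 is 0.17.

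### The exchangeable working correlation that D.2 fixes for its GEE accuracy measures pulls per-vessel PPV (and slightly NPV) away from the 2×2 value when disease clusters within patients

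*Combined protocol and SAP*

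**What the plan says.** Section D.2 states: "Sensitivity, specificity, accuracy, negative predictive value and positive predictive value will be estimated by using generalized estimating equations". The same sentence adds the dependence assumption: "assuming that all measurements in each individual vessel and for each person will be correlated interchangeably". The protocol does not say whether each measure is fitted separately within its subset (for PPV, the CT-positive vessels) or as a regression over all vessels. It mentions no independence structure, no robust variance and no sensitivity analysis.

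On the unit of analysis, D.2 ends: "The analysis includes patient-based analysis and coronary artery-based analysis". The 17-segment level appears under Image Analysis in D.1, where quantitative analysis of the perfusion scans is "performed on per segment (AHA 17 segment model), per territory, per slice and per patient basis". D.2 does not say that the GEE is applied to segments.

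On case mix, D.1 states: "The goal is to include 30 patients, of which 15 should have significant CAD". No expected accuracy and no figure for within-patient clustering is given.

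**The concern.** GEE with any working correlation other than independence needs more than a correct mean model. A vessel's expected outcome, given the covariates of all the patient's vessels, must equal its expectation given its own covariate alone. For PPV and NPV this fails when disease clusters. A CT-positive vessel is more likely to be truly PET-positive if its neighbours are also CT-positive.

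This concerns the point estimate, not the width of the interval, and more patients do not cure it. Specific Aim 3 is about diagnostic accuracy and PPV is a named measure. The PPV reported from the model would disagree with the PPV read off the study's own per-vessel 2×2 table, usually on the low side.

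**Working it through.** **Inputs.** From the protocol: GEE with an exchangeable correlation, and 30 patients of whom 15 should have significant CAD. There is no figure of the plan's own to reproduce. The following are assumed:
- three vessels per patient;
- sensitivity 0.80 and specificity 0.90, with CT errors independent given the vessel's own PET status;
- 1, 2 or 3 diseased territories in 50%, 30% and 20% of PET-positive patients;
- 50% of patients PET-positive (in line with 15 of 30), or 30%.

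**Step 1: the 2×2 value.** Diseased vessels per PET-positive patient: 0.5×1 + 0.3×2 + 0.2×3 = 1.7.
- 50% PET-positive: prevalence 0.5×1.7/3 = 0.283. PPV = 0.80×0.283 / (0.80×0.283 + 0.10×0.717) = 0.760.
- 30% PET-positive: prevalence 0.170. PPV = 0.136 / (0.136 + 0.083) = 0.621.

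**Step 2: does the GEE condition hold for PPV?** Take 50% PET-positive. The patient probabilities of 0, 1, 2 and 3 diseased vessels are 0.50, 0.25, 0.15 and 0.10.

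The probability that all three vessels are CT-positive is 0.50×0.001 + 0.25×0.80×0.01 + 0.15×0.64×0.10 + 0.10×0.512 = 0.0633. The expected number of diseased vessels among them is 1×0.0020 + 2×0.0096 + 3×0.0512 = 0.1748. The share diseased is 0.1748/(3×0.0633) = 0.92. The same enumeration for one and two CT-positive vessels gives:

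| CT-positive vessels in patient (n) | Probability | Share of them PET-positive |
|---|---|---|
| 1 | 0.3459 | 0.621 |
| 2 | 0.1796 | 0.808 |
| 3 | 0.0633 | 0.920 |

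The chance that a CT-positive vessel is diseased depends strongly on the other vessels' CT results, so the condition fails.

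**Step 3: separate model within CT-positive vessels.** Each patient has weight n/(1+(n−1)ρ). The moment estimate is ρ = 0.233, so the weights are 1, 1.62 and 2.05 instead of 1, 2 and 3.
- Exchangeable: (0.3459×1×0.621 + 0.1796×1.62×0.808 + 0.0633×2.05×0.920) / (0.3459×1 + 0.1796×1.62 + 0.0633×2.05) = 0.569/0.767 = 0.74.
- Independence (weights 1, 2, 3): 0.680/0.895 = 0.76, the 2×2 value.

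**Step 4: both model forms.** The joint model regresses PET status on CT result over all vessels. Its limits were found by solving the estimating equations over the same enumerated outcomes. Its range reflects whether the scale is fixed at 1 or estimated.

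| PET-positive patients | Measure | 2×2 | Separate model | Joint model |
|---|---|---|---|---|
| 50% | PPV | 0.760 | 0.743 | 0.723–0.726 |
| 30% | PPV | 0.621 | 0.570 | 0.546–0.555 |
| 50% | NPV | 0.919 | 0.915 | 0.909–0.910 |
| 30% | NPV | 0.957 | 0.954 | 0.947–0.948 |

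Simulations on these inputs agree: 0.76 becomes 0.74 or 0.72, and 0.62–0.63 becomes 0.57–0.58 or 0.55.

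**Step 5: sensitivity and specificity.** Here PET status is the covariate. Under the same inputs a PET-positive vessel is CT-positive with probability 0.80 whatever the other vessels show. So ρ = 0, and both model forms return exactly 0.800 and 0.900. A patient random effect of SD 1 on CT errors, unrelated to disease, moved sensitivity by 0.001 or less.

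**Step 6: other assumptions.**
- Sensitivity and specificity 0.85, each vessel of a CAD patient diseased with probability 0.5: PPV 0.677 becomes 0.660 (separate) or 0.657 (joint).
- Separate model, sensitivity and specificity 0.70–0.95, within-patient disease probability 0.3–0.7: PPV shift from 0 to −0.054.
- CT errors also correlated within patient: PPV shift only −0.001 to −0.005.
- Largest simulated per-vessel shift: 0.63 to 0.55, that is −0.08.
- Disease not clustered: no shift in any measure.

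**Step 7: 30 patients.** In simulation on the step 1 inputs, the mean per-vessel PPV was 0.76 with independence and 0.72–0.74 with exchangeable. Its SD was 0.100 with independence and 0.106–0.118 with exchangeable.

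**The case against.** **The effect is small for this study.** D.2 describes it this way: "This is a preliminary and pilot study, with a convenience sample of 30 patients, that we deem adequate to demonstrate our hypothesis". At the vessel level the sampling SD of PPV exceeds the shift, and with correlated CT errors the shift nearly vanishes. This stands, and it limits the importance of the point. It is not a reason to keep the assumption, because for PPV the exchangeable fit was also the more variable one in step 7.

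**It is a choice of target.** Exchangeable weighting in the separate model moves PPV towards a patient average, and D.2 does not say which average it wants. This stands only in part. On the step 2 figures the patient average is (0.3459×0.621 + 0.1796×0.808 + 0.0633×0.920)/0.5888 = 0.71. The exchangeable limit of 0.74 is neither that nor the pooled 0.76, and the joint model targets neither by design.

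**Stronger readings that the documents do not support.** A reader might infer that clustered PET disease also biases sensitivity. Step 5 shows that it does not. That would need sensitivity to vary with the extent of disease in the patient, on which the protocol is silent. In one assumed scenario of that kind the per-vessel shift was 0.004; in another, with errors also clustered, 0.85 became 0.84.

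A reader might also infer a much larger PPV error from the 17 segments. In simulation, segment PPV went from 0.62 to 0.52 or 0.46, and shifts of up to about −0.17 arose. These apply only if the GEE is run on segments, which D.2 does not state.

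**Conclusion.** The concern holds for PPV and, slightly, for NPV in the coronary artery-based analysis. If disease clusters within patients, the prescribed correlation does not recover the per-vessel PPV, whatever the sample size. The shift is 0 to about −0.08 for PPV and about one point or less for NPV.

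The direction and mechanism are firm. The sizes rest on assumed accuracy and clustering, on reading the D.2 wording as an exchangeable working correlation, and on the pooled per-vessel proportion as the target.

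Sensitivity and specificity are not biased by clustered disease alone. The patient-level analysis has one unit per cluster and is untouched. The change should be made because it is cheap and improves a named measure, not because it would overturn a conclusion from 30 patients.

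**What to change.** In D.2, replace the interchangeable-correlation assumption by: *an independence working correlation, with the patient as the cluster and patient-clustered robust variance*. It is needed for PPV and NPV and safe for all five measures. The point estimates then equal the 2×2 proportions, and the clustering is carried by the standard errors. If the GEE is also meant for territories or segments, D.2 should say so and apply the same rule there.

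The cost is one sentence and one software option, with a possible small loss of efficiency for some measures.
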